- ∀ Data and Safety Monitoring Board (DSMB): The DSMB will conduct periodic reviews of safety data from all enrolled participants throughout the clinical study. The DSMB will make recommendations to the sponsor, based on these data, on the future conduct of the clinical study and in particular on whether to continue, terminate, or modify the clinical study.
- ∀ Independent Efficacy Review Group: This group will be independent of the study team and will review, interpret, and make decisions on future conduct of the clinical study based on the proposed interim analyses for futility and efficacy and on any additional analyses carried out for administrative purposes.
- ∀ Rapidly Progressive Osteoarthritis (RPOA) Adjudication Committee (RPOA-AC): The role of this committee is to independently review, interpret, and adjudicate possible or probable joint safety events including but not limited to RPOA, subchondral insufficiency fracture, primary osteonecrosis, or pathological fracture cases that are experienced by the study participants. The RPOA-AC will review and adjudicate all treatment-emergent joint safety events that meet SAE or severe AE criteria or which led to joint replacement or other arthroplasty procedures.

Statistical Methods

An 'attributable' estimand strategy will be adopted for primary endpoint data missing or affected by any of the following 4 intercurrent events:

- \forall Discontinuation due to lack of efficacy or an adverse event
- \forall Discontinuation due to other reasons such as loss to FU or external circumstances
- \forall Taking prohibited pain medication during the treatment period
- \forall Taking excessive permitted rescue medication

Missing or affected primary endpoint values will be imputed, but the method of imputation will differ depending upon the intercurrent event.

Analysis Populations

- ∀ Screening set: This set includes all participants who provide informed consent and/or assent and provide demographic and/or baseline screening assessments, regardless of the participant's randomisation and treatment status in the study.
- ∀ Full analysis set: This set will be used for all efficacy analyses, and it is defined according to the intent-to-treat principle as including all randomised participants.

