9 STATISTICAL CONSIDERATIONS

9.1 Statistical Hypotheses

Formal statistical testing is designed to preserve the overall family-wise type-error at 1-sided $\alpha = 0.025$.

Multiple Comparison Procedure-Modelling Statistical Tests

The multiple comparison stage of the Multiple Comparison Procedure-Modelling (MCP-Mod) analysis will test for the primary endpoint 'Change in the weekly average of daily NRS pain scores from baseline to Week 12' the global null hypothesis of no dose-response effect, ie, the linear contrasts of group means corresponding to each of the 6 prespecified candidate dose-response models are all identically zero.

The analysis will be performed at the 1-sided type-1 error of $\alpha = 0.025$. The minimum of the multiplicity adjusted p-values corresponding to each candidate model will be used as the basis for concluding statistical significance.

Pairwise statistical tests

For primary and key secondary endpoints, pairwise analyses will test for each dose versus placebo the null hypothesis of no treatment effect, ie, MEDI7352 dose - placebo = 0.

Pairwise testing of prespecified MEDI7352 doses versus placebo of the primary and key secondary endpoints will be performed using a sequentially rejective multiple comparison approach to ensure overall family-wise type 1 error across primary and key secondary endpoints is controlled at 1-sided $\alpha = 0.025$ (Bretz et al 2009).

The testing process will commence with the primary endpoint and testing of the key secondary endpoints will only be considered if statistical significance is demonstrated for the primary endpoint.

Further details of the multiplicity testing strategy, including the doses considered for testing, the form of the consonant component tests, and their respective weights will be prespecified in the statistical analysis plan (SAP), which will be finalised before the first interim analysis.

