9.2 Sample Size Determination

Approximately 350 eligible participants will be randomly assigned to double-blind treatment with one of 4 dose levels of MEDI7352 or placebo. Recruitment will continue until the planned unconditional power of the study is achieved (ie, when statistical information equivalent to 255 participants completing the treatment period is reached or approximately 350 randomised participants, whichever is sooner. The statistical information will be calculated based upon ongoing blinded study data. Further details will be given in the Statistical Analysis Plan.

With statistical information equivalent to 255 evaluable participants, the study will have greater than 90% power to detect a statistically significant (at overall 1-sided $\alpha = 0.025$) dose-response relationship using a MCP-Mod approach for the primary endpoint: Change in the weekly average of daily NRS pain scores from baseline to Week 12. This assumes that the true Week 12 placebo-corrected change from baseline difference at the CCI dose is 1.5, the true dose-response follows a maximum response (Emax) relationship with a dose that produces half of the E_{max} (ED₅₀) = CCI and a SD = 2.4.

The 6 candidate dose response models incorporated into the MCP-Mod test were chosen to reflect potential convex, linear, and concave dose-response relationships and are as follows:

- \forall Three convex E_{max} models with increasing ED₅₀: ^{CCI}
- \forall One model linear in dose
- \forall Two concave exponential models defined by 10% and 25% of the maximum drug effect at CCI

The above calculations were performed using the software R and the R-package 'DoseFinding' [https://cran.r-project.org/web/packages/DoseFinding/DoseFinding.pdf]

9.3 **Populations for Analyses**

The following populations are defined (Table 9):

Population/Analysis set	Description
Screening set	This set includes all participants who provide informed consent and/or assent and provide demographic and/or baseline screening assessments, regardless of the participant's randomisation and treatment status in the study.

Table 9Populations for Analysis

Population/Analysis set	Description
Full analysis set	This set will be used for all efficacy analyses, and it is defined according to the intent-to-treat principle as including all randomised participants.

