9.5 Interim Analyses

The study incorporates 2 interim analyses: (1) a futility analysis will take place when approximately 25% of participants are evaluable for the primary endpoint; this analysis will assess the likely success of the study outcome and will enable the sponsor to make a go/no-go decision regarding continuation of the study; and (2) an interim analysis of efficacy data will take place when approximately 50% of participants are evaluable for the primary endpoint; this analysis will enable the sponsor to plan future project-related activities, but without making any changes to the current study.

No alpha adjustment is required for the interim analyses because early stopping for efficacy is not a feature of the study design.

Unblinded personnel who are not otherwise involved in the study will prepare the data for review by the Independent Efficacy Review Group, who are themselves independent of the day-to-day study activities. The study team will remain blinded to the results of the interim analyses for the duration of the study. Firewalls will be put in place to ensure that information is not inadvertently disseminated.

The interim SAP will describe the planned interim analyses in greater detail.

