The role of the Independent Efficacy Review Group is to independently review, interpret and adjudicate on the proposed interim analyses for futility and efficacy and on any additional analyses carried out for administrative purposes. The group will make recommendations to the study team, based on these analyses, on the future conduct of the trial and in particular on whether to continue, terminate or modify the study. To do so, the group will make their recommendations on the basis of access to unblinded data at both the participant and treatment group level. Along with a recommendation, the group will provide sufficient contextual information such that the study team can determine whether and how to implement the recommendation.

The Independent Efficacy Review Group will consist of sponsor personnel who are independent of the study team.

The membership, responsibilities, and procedures applicable to the Independent Efficacy Review Group will be detailed in its charter.

Rapidly Progressive Osteoarthritis Adjudication Committee

The role of the Rapidly Progressive Osteoarthritis Adjudication Committee (RPOA-AC) is to independently review, interpret, and adjudicate possible or probable joint safety events including but not limited to RPOA, SIF, primary osteonecrosis, or pathological fracture cases that are experienced by the study participants. The RPOA-AC will review and adjudicate all joint safety events that meet SAE or severe AE criteria or AEs that led to joint replacement or other arthroplasty procedures to determine whether or not they meet accepted diagnostic criteria. Joint safety events will be identified preliminarily by the investigators, and also by AstraZeneca/sponsor personnel or during the RPOA-AC process as specified in the committee's charter. The RPOA-AC member/s will not have access to individual treatment codes for any participant and will remain blinded to treatment throughout the study duration.

Causality assessments will also be made by the RPOA-AC in a blinded fashion. The committee will not possess governance authority, but its adjudication and opinion will be considered in relation to prespecified stopping criteria in the protocols

The objectives for performing the adjudication of cases from study D5680C0003 are to:

- ∀ Gain the adjudicators' agreement on the definition of possible or probable RPOA (type 1 and type 2), SIF, primary osteonecrosis, or pathological fracture cases.

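### Appendix B 5 gives the Independent Efficacy Review Group a remit, and a line to the study team, that contradict Section 9.5 and undermine the basis for making no alpha adjustment

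*Protocol*

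**What the plan says.** **Section 9.5 (its account of the two looks is repeated in the Synopsis and Section 4.1).** The look at about 25% evaluable is for futility and supports a sponsor go/no-go decision. The look at about 50% uses efficacy data, serves planning of later project work, and is to leave the present study unchanged. On error control: "No alpha adjustment is required for the interim analyses because early stopping for efficacy is not a feature of the study design". On blinding: "The study team will remain blinded to the results of the interim analyses for the duration of the study", with firewalls.

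**Appendix B 5.** The Independent Efficacy Review Group consists of sponsor personnel outside the study team. It sees unblinded data at participant and group level. On the futility analysis, the efficacy analysis and any additional administrative analyses, it makes recommendations to the study team "on the future conduct of the trial and in particular on whether to continue, terminate or modify the study". It adds that "the group will provide sufficient contextual information such that the study team can determine whether and how to implement the recommendation".

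**Synopsis, Data Monitoring Committees.** The group will "make decisions on future conduct of the clinical study based on the proposed interim analyses for futility and efficacy".

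**Section 9.6.** The group reviews, interprets and adjudicates; no power to modify is mentioned.

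**The concern.** Four points conflict.

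1. **The 50% look.** Section 9.5 allows it no effect on this study. Appendix B 5 allows a recommendation to terminate or modify on the efficacy analysis.
2. **The 25% look.** Section 9.5 gives it two outcomes, go or no-go. Modification is a third that Section 9.5 does not provide.
3. **Blinding.** Section 9.5 keeps the study team blinded to interim results. Appendix B 5 makes that team the recipient of the recommendation and of enough context to judge how to act on it. This is the sharpest conflict.
4. **Role.** The group decides (Synopsis), recommends (Appendix B 5) or adjudicates (Section 9.6).

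The case for making no alpha adjustment depends on the looks not altering the trial in favour of an efficacy claim. Following Appendix B 5 would permit a design change driven by unblinded efficacy data, with no stated method of error control. It could also let interim information reach people running a trial with a patient-reported pain endpoint.

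**Working it through.** **Inputs from the protocol.** One-sided alpha 0.025 (Section 9.1); information equivalent to 255 evaluable participants, effect 1.5, SD 2.4 (Section 9.2); five equal arms, so 255 / 5 = 51 per arm; looks at 25% and 50% (Section 9.5).

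**Step 1. The plan's own power figure.** Section 9.2 states: "With statistical information equivalent to 255 evaluable participants", "the study will have greater than 90% power to detect a statistically significant" dose response.

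- Simple anchor, effect 1.5 at one dose against placebo: standard error = 2.4 × √(2/51) = 0.475; 1.5 / 0.475 = 3.156; power = Φ(3.156 − 1.960) = 0.884.
- Maximum of six contrasts (three Emax, linear, two exponential), by simulation. The doses and shape parameters are redacted, so this assumes the 15:50:150:300 spacing of the IV equivalents in Section 4.3, the 1.5 effect at the top dose, and a true ED50 between 5 and 300 on that scale. Power is 0.916 to 0.946.

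The stated power is reproduced within those assumptions and is not in question.

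**Step 2. Type I error if Section 9.5 is followed.** A futility stop can only remove rejections. As an illustration, assume the trial stops if Z < 0 at 25% information. The correlation of that Z with the final Z is √0.25 = 0.5.

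P(Z_final > 1.96 and Z_25 > 0) = 0.025 − P(Z_final > 1.96 and Z_25 < 0) = 0.025 − 0.0023 = 0.0227.

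The 50% look then changes nothing. The error is at or below 0.025, as the protocol claims.

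**Step 3. Type I error if Appendix B 5 were used to stop and claim efficacy at 50%.** This is hypothetical. With 1.96 at both looks and correlation √0.5 = 0.707:

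P(Z_50 > 1.96 or Z_final > 1.96) = 0.025 + 0.025 − P(both) = 0.050 − 0.0084 = 0.0416.

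The same calculation for the maximum-contrast test, with assumed candidate shapes, gives 0.042.

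**Step 4. Stopping at 50% without a claim.** No null hypothesis is rejected, so nothing is added to the type I error.

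**Step 5. The texts side by side.**

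| Question | Section 9.5 | Appendix B 5 | Synopsis, committees |
|---|---|---|---|
| Outcomes at 25% | go or no-go | continue, terminate, modify | decisions on conduct |
| Outcomes at 50% | none for this study | continue, terminate, modify | decisions on conduct |
| What the study team receives | no interim results | recommendation plus context | not stated |
| Who acts | sponsor, at 25% | study team chooses whether to implement | the group |

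Only continuing or terminating at 25% is common ground.

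**The case against.** The strongest reply is that the main text is explicit and repeated, and that the appendix wording looks carried over. The DSMB paragraph of Appendix B 5 uses nearly the same sentences, except that its recommendations go to the sponsor. The group's charter and the interim SAP, neither at hand, are to give procedures. Much of this stands:

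- Terminating after the 25% look agrees with the go/no-go role and does not inflate alpha.
- Membership by sponsor staff is no contradiction. Section 9.5 asks for independence from day-to-day study activities.
- The recruitment rule in Section 9.2 already uses blinded data.
- The protocol does not say that the contextual information discloses results.

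A reader might go further and infer that the alpha statement is void and the error rate really is 0.042, or 0.057 with unadjusted efficacy claims at 25%, 50% and the end. The documents do not support that. No section provides an interim efficacy claim or boundary, and the 25% look is for futility only. A reader might also infer 0.028 from an unblinded choice of final size between 255 and 350. That mixes units: 255 is evaluable-equivalent information, 350 is a cap on randomised participants, and recruitment ends at whichever comes sooner. Nor does the text establish that the study team would in fact be unblinded.

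What the reply does not remove is the conflict in current text. A charter or interim SAP can add detail, but should not have to choose between two opposed protocol statements.

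**Conclusion.** Appendix B 5 contradicts Section 9.5 on what may follow the 50% look, on modification at either look, and on what reaches the study team; the Synopsis adds a conflict on who decides. This undermines the no-adjustment statement without voiding it. Type I error is at or below 0.025 if Section 9.5 is followed. It would be about 0.042 only under the assumption that efficacy is claimed at an unadjusted one-sided 0.025 at exactly half the information and again at the end. An unblinded modification would also fall outside any stated error control; its size cannot be given because no modification is defined. The point must be corrected because following the appendix as written would allow what Section 9.5 rules out.

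**What to change.** Amend Appendix B 5 and the Synopsis to match Section 9.5, and align the role wording in Section 9.6:

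- At 25%, the group returns only continue or stop for futility, without results, to a sponsor body outside the blinded study team.
- The 50% look and any administrative analyses yield no recommendation on this study.
- Delete the option to modify, and delete the sentence on contextual information for the study team.
- State that the end of recruitment, already based on blinded data, is decided by staff without access to interim results.

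The cost is wording in the protocol and matching text in the group's charter. It needs no extra patients or data, and the sponsor gives up only options that Section 9.5 already disclaims.

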Appendix D Handling of Human Biological Samples

D 1 Chain of Custody

A full chain of custody is maintained for all samples throughout their life cycle.

The investigator at each study site keeps full traceability of collected biological samples from the participants while in storage at the centre until shipment or disposal (where appropriate) and records relevant processing information related to the samples while at site.

The sample receiver keeps full traceability of the samples while in storage and during use until used or disposed of or until further shipment and keeps record of receipt of arrival and onward shipment or disposal.

AstraZeneca or delegated representatives will keep oversight of the entire life cycle through internal procedures, monitoring of study sites, auditing or process checks, and contractual requirements of external laboratory providers.

Samples retained for further use will be stored in the AstraZeneca-assigned biobanks or other sample archive facilities and will be tracked by the appropriate AstraZeneca team during the entire life cycle.

If required, AstraZeneca will ensure that remaining biological samples are returned to the site according to local regulations or at the end of the retention period, whichever is sooner.

D 2 Withdrawal of Informed Consent for Donated Biological Samples

If a participant withdraws consent to the use of donated biological samples, the samples will be disposed of/destroyed/repatriated, and the action documented. If samples are already analysed, AstraZeneca is not obliged to destroy the results of this research.

Following withdrawal of consent for biological samples, further study participation should be considered in relation to the withdrawal processes outlined in the informed consent.

The investigator:

- ∀ Ensures participant's withdrawal of informed consent to the use of donated samples is highlighted immediately to AstraZeneca.
- ∀ Ensures that biological samples from that participant, if stored at the study site, are immediately identified, disposed of as appropriate, and the action documented.
- ∀ Ensures that the participant and AstraZeneca are informed about the sample disposal.
- ∀ Ensures the organisation(s) holding the samples is/are informed about the withdrawn consent immediately and that samples are disposed of/destroyed, the action documented, and the signed document returned to the study site.

D 3 International Airline Transportation Association 6.2 Guidance Document

LABELLING AND SHIPMENT OF BIOHAZARD SAMPLES

International Airline Transportation Association (IATA)

(https://www.iata.org/whatwedo/cargo/dgr/Pages/download.aspx) classifies infectious substances into 3 categories: Category A, Category B or Exempt

Category A infectious substances are infectious substances in a form that, when exposure to it occurs, is capable of causing permanent disability, life-threatening or fatal disease in otherwise healthy humans or animals.

Category A pathogens are, eg, Ebola, Lassa fever virus. Infectious substances meeting these criteria which cause disease in humans or both in humans and animals must be assigned to UN 2814. Infectious substances which cause disease only in animals must be assigned to UN 2900.

Category B infectious substances are infectious substances that do not meet the criteria for inclusion in Category A. Category B pathogens are, eg, Hepatitis A, C, D, and E viruses. They are assigned the following UN number and proper shipping name:

- ∀ UN 3373 Biological Substance, Category B
- \forall To be packed in accordance with UN 3373 and IATA 650

Exempt - Substances which do not contain infectious substances or substances which are unlikely to cause disease in humans or animals are not participant to these regulations unless they meet the criteria for inclusion in another class.

- ∀ Clinical study samples will fall into Category B or exempt under IATA regulations
- Clinical study samples will routinely be packed and transported at ambient temperature in IATA 650 compliant packaging (https://www.iata.org/whatwedo/cargo/dgr/Documents/DGR-60-EN-PI650.pdf).
- ∀ Biological samples transported in dry ice require additional dangerous goods specification for the dry-ice content

Appendix E Optional Genomics Initiative Sample

E 1 Use/Analysis of DNA

Genetic variation may impact a participant's response to therapy, susceptibility to, and severity and progression of disease. Variable response to therapy may be due to genetic determinants that impact drug absorption, distribution, metabolism, and excretion; mechanism of action of the drug; disease aetiology; and/or molecular subtype of the disease being treated. Therefore, where local regulations and Institutional Review Board/Independent Ethics Committee (IRB/IEC) allow, a blood sample will be collected for DNA analysis from consenting participants.

AstraZeneca intends to collect and store DNA for genetic research to explore how genetic variations may affect clinical parameters, risk and prognosis of diseases, and the response to medications. This genetic research may lead to a better understanding and diagnosis of diseases or other improvements in health care and to the discovery of new diagnostics, treatments, or medications. Therefore, where local regulations and IRB/IEC allow, a blood sample will be collected for DNA analysis from consenting participants.

This optional genetic research may consist of the analysis of the structure of the participant's DNA, ie, the entire genome.

The results of genetic analyses may be reported in a separate study summary.

The sponsor will store the DNA samples in a secure storage space with adequate measures to protect confidentiality.

E 2 Genetic Research Plan and Procedures

Selection of Genetic Research Population

All participants will be asked to participate in this genetic research. Participation is voluntary, and if a participant declines to participate, there will be no penalty or loss of benefit. The participant will not be excluded from any aspect of the main study.

Inclusion Criteria

For inclusion in this genetic research, participants must fulfil all of the inclusion criteria described in the main body of the clinical study protocol (CSP) and provide informed consent for the Genomics Initiative sampling and analyses.

Exclusion Criteria

Exclusion from this genetic research may be for any of the exclusion criteria specified in the main study or any of the following:

- ∀ Previous allogeneic bone marrow transplant
- ∀ Non-leukocyte-depleted whole blood transfusion in 120 days of genetic sample collection
- ∀ No Genomics Initiative samples to be collected from healthy volunteers and paediatric participants.

Withdrawal of Consent for Genetic Research

Participants may withdraw from this genetic research at any time, independent of any decision concerning participation in other aspects of the main study. Voluntary withdrawal will not prejudice further treatment. Procedures for withdrawal are outlined in Section 7.2 of the main CSP.

Collection of Samples for Genetic Research

A 6 mL K2 ethylenediaminetetraacetic acid blood sample will be collected for the Genomics Initiative sample.

The blood sample for this genetic research will be obtained from the participants at Visit 1 specified in the schedule of assessments (Table 1). Although DNA is stable, early sample collection is preferred to avoid introducing bias through excluding participants who may withdraw due to an adverse event (AE). If for any reason the sample is not drawn at Visit 1, it may be taken at any visit until the last study visit. Only one sample should be collected per participant for genetics during the study.

Coding and Storage of DNA Samples

The processes adopted for the coding and storage of samples for genetic analysis are important to maintain participant confidentiality. Samples will be stored for a maximum of 15 years, from the date of last participant last visit, after which they will be destroyed. DNA is a finite resource that is used up during analyses. Samples will be stored and used until no further analyses are possible or the maximum storage time has been reached.

An additional second code will be assigned to the sample either before or at the time of DNA extraction replacing the information on the sample tube. Thereafter, the sample will be identifiable only by the second, unique number. This number is used to identify the sample and corresponding data at the AstraZeneca genetics laboratories, or at the designated organisation. No personal details identifying the individual will be available to any person (AstraZeneca employee or designated organisations working with the DNA).

The link between the participant enrolment/randomisation code and the second number will be maintained and stored in a secure environment, with restricted access at AstraZeneca or designated organisations. The link will be used to identify the relevant DNA samples for

analysis, facilitate correlation of genotypic results with clinical data, allow regulatory audit, and permit tracing of samples for destruction in the case of withdrawal of consent.

Ethical and Regulatory Requirements

The principles for ethical and regulatory requirements for the study, including this genetics research component, are outlined in Appendix B.

Informed Consent

The genetic component of this study is optional and the participant may participate in other components of the main study without participating in this genetic component. To participate in the genetic component of the study, the participant must sign and date both the consent form for the main study and the addendum for the Genomics Initiative component of the study. Copies of both signed and dated consent forms must be given to the participant and the original filed at the study centre. The Principal investigator(s) is responsible for ensuring that consent is given freely and that the participant understands that he/she may freely withdrawal from the genetic aspect of the study at any time.

Subject Data Protection

AstraZeneca will not provide individual genotype results to participants, any insurance company, any employer, participant's family members, or participant's general physician unless required to do so by law.

Extra precautions are taken to preserve confidentiality and prevent genetic data being linked to the identity of the participant. In exceptional circumstances, however, certain individuals might see both the genetic data and the personal identifiers of a participant. For example, in the case of a medical emergency, an AstraZeneca physician or an investigator might know a participant's identity and also have access to his or her genetic data. Regulatory authorities may require access to the relevant files, though the participant's medical information and the genetic files would remain physically separate.

Data Management

Any genetic data generated in this study will be stored at a secure system at AstraZeneca and/or designated organisations to analyse the samples.

AstraZeneca and its designated organisations may share summary results (such as genetic differences from groups of individuals with a disease) from this genetic research with other researchers, such as hospitals, academic organisations, or health insurance companies. This can be done by placing the results in scientific databases, where they can be combined with the results of similar studies to learn even more about health and disease. The researchers can only use this information for health-related research purposes. Researchers may see summary results but they will not be able to see individual participant data or any personal identifiers.

Some or all of the clinical datasets from the main study may be merged with the genetic data in a suitable secure environment separate from the clinical database.

Statistical Methods and Determination of Sample Size

The number of participants who will agree to participate in the genetic research is unknown. It is therefore not possible to establish whether sufficient data will be collected to allow a formal statistical evaluation or whether only descriptive statistics will be generated. A statistical analysis plan may be prepared where appropriate.

